3 OBJECTIVES AND OUTCOME MEASURES

3.1 Primary

Objective	Brief Description/Justification of Outcome Measure	Outcome Measured By	Time Frame

To quantify the incidence and prevalence of biologic complications amongst patients receiving dental implant therapy in a private practice setting.
	
Biologic complications will be defined as an implant that presented with measured bone loss on the radiographs and/or bleeding on probing, or failed implant. Biologic complications will be defined as a) Peri-implant mucositis: Bleeding on Probing (BoP) and/or purulent exudate without measured bone loss, or b) Peri-implantitis: measured bone loss on the radiographs, or c) Implant failure: an implant that has been lost or is planned to be removed
 
Incidence estimation will be based on a Poisson model for incidence per implant and year of follow-up.
	
a) The presence or absence of Bleeding on Probing (BoP) is measured by the practitioners at the annual evaluation visits and recorded in the annual follow-up surveys.
 
b) The radiographic bone changes are measured on the radiographs by calibrated examiners, utilizing the known geometry of the implant to convert to mm of bone change. Bone loss is defined as the negative change of the bone level measurements from the baseline radiographs taken at the time of prosthetic insertion.
 
c) Implant Failure: absence or planned removal of implant
	
Baseline data are collected at the time of prosthesis insertion and at each of the three annual follow-up visits.
 
The radiographs taken for clinical care purposes at prosthesis insertion and the 1, 2 and 3-year follow-up visits that are approved by the study team to be added to the radiograph repository will be utilized for radiographic assessments.

Objective	Brief Description/Justification of Outcome Measure	Outcome Measured By	Time Frame

To quantify the incidence and prevalence of prosthetic
	
Prosthetic complications will be defined as any complication that has compromised the esthetics
	
At baseline, practitioners will record surgical data (implant brand, size
	
Baseline surgical and specific prosthetics data

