7.3 Radiographic Assessment

One trained and calibrated periodontist will first assess diagnostic quality of submitted images. High quality radiographic images should include the following:

- The radiograph should capture the complete length of the implant
- The radiograph should show the most coronal aspect of the crestal bone adjacent to the implant
- The buccal and lingual cusp of the posterior teeth should be aligned and overlap each other
- The contact points between the teeth must not overlap each other
- The image must be sharp and of good contrast

The quality of the radiograph will be assessed by the study team. If the radiograph is of acceptable projection geometry as outlined above the radiograph will be used for analysis. For radiographs that do not meet the above criteria feedback will be provided to the Node Coordinator to pass along to the practitioner to correct the acquisition of future radiographs.

Only Radiographs that are determined to be of sufficient quality will go into the radiograph repository. Every radiograph in the radiograph repository will go through the adjudication process, where two trained and calibrated evaluators assess the radiograph for quality. Two initial evaluators will measure the peri-implant bone height, emergence angle, and prosthetic fit, as described in the following sections. The NCC's adjudication system will compare these measurements and notify a third evaluator if the measurements taken by the initial evaluators vary too much from each other. If the measurements taken by the third evaluator vary too much from both initial evaluators, a panel review consisting of the three evaluators will take place. With the exception of the panel review, the evaluators are blinded to each other's measurements. Each evaluator will upload a marked radiograph into the NCC's adjudication system.

Peri-implant bone height

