Bone height will be measured utilizing the known geometry of the implant to convert to mm of bone change. The evaluations will be used to provide confirmation of bone loss, which is defined as the negative change of the bone level measurements from the baseline radiographs taken at the time of prosthetic insertion. Alveolar bone levels will be measured at mesial and distal sites of study implants on all images as the distance between platform of the implant and alveolar bone crest. All measurements will be made in pixels. The unit pixel is merely a digital measurement unit and varies with the resolution with which the image was saved or scanned. For conversion back to millimeters, a known dimension needs to be represented on an image. The implant length or diameter will serve as known entity on the radiographs, and each implant will be measured. The custom conversion for each image utilizing the measured implant length in pixels by the known implant length or spacing between the threads in millimeters. This method allows for the comparison between images taken with different systems and makes the changes clinically relevant as they are expressed in millimeters. Image processing software will be used to capture measurements from the radiographic images.

Measurement of the emergence angle

The mesial and distal emergence angle of the prosthesis will be measured using the implant platform as the vertex, with one ray following the long axis of the implant and the other aligned with the gingival contour of the implant abutment.

Prosthetic fit

The presence of a gap between the abutment and the implant and/or the abutment and the prosthesis will be recorded.

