The unit of analysis for the secondary objectives are at the implant level for the biologic complications and the prosthesis level for the prosthetic complications. All the outcomes are binary outcomes (Y/N), and for primary analysis only the first occurrence will be considered. Multiple implants/ prostheses are clustered within the same patient, and multiple patients clustered within practitioners. To account for these correlations, General Estimating Equations (GEE) will be used to identify practitioner, patient and implant variables that are associated with the complications. A binomial model with a logit link function will be used for these binary outcomes. Separate analyses will be conducted for each complication. The variables in table 3 will be considered as potential risk factors.

Secondary analysis will evaluate the association between patient/implant/prosthetic risk factors and the rates of repeated prosthetic complications and the disease progression in biologic complications. For the rates of prosthetic complications, the outcome will be the number (count) of prosthetic complications during the 3-year follow-up period. The unit of analysis will be at the person level, and Poisson models will be used to identify practitioner, patient and prosthesis risk factors that are associated with a higher rate of prosthetic complications. For disease progression in biologic complications, the outcome will be mm bone loss (continuous) over time. Mixed effects model will be used to

account for the longitudinal nature of the data and to identify the practitioner, patient and implant risk factors that are associated with a higher amount of bone loss.

Table 3.

Practitioner level factors	
Number of implants restored per month	biologic and prosthetic complications
Years in practice	biologic and prosthetic complications
Post graduate education	biologic and prosthetic complications
Specialty training	biologic and prosthetic complications
Patient level risk factor	outcome
Age at baseline	biologic and prosthetic complications
Diabetes Mellitus	biologic complications
Smoking status	biologic complications
Medication use SSRI Bone sparing drugs Corticosteroid use	biologic complications
Osteoporosis	biologic complications
Radiation therapy	biologic complications
Periodontitis diagnosis	biologic complications
Gingivitis diagnosis	biologic complications
Parafunctional habits	prosthetic complications
Implant/ Prosthesis level risk factor	

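### Bone-loss progression is analysed as change from the baseline film, so implants without an accepted baseline film have no observed outcome even though their later bone levels are measured

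*Protocol*

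**What the plan says.** - Outcome and model (Protocol 11.3, Secondary Objectives): "For disease progression in biologic complications, the outcome will be mm bone loss (continuous) over time". The next sentence begins "Mixed effects model will be used to" and goes on to the longitudinal structure and the search for practitioner, patient and implant risk factors.
- Definition (Protocol 3.1): "Bone loss is defined as the negative change of the bone level measurements from the baseline radiographs taken at the time of prosthetic insertion". Section 7.3 repeats it: bone loss is "defined as the negative change of the bone level measurements from the baseline radiographs taken at the time of prosthetic insertion". No other definition is given.
- Measurement (Protocol 7.3): "Alveolar bone levels will be measured at mesial and distal sites of study implants on all images". The quantity is the platform-to-crest distance, converted to mm, so each measured film yields a bone level in its own right.
- Quality screen (Protocol 7.3): "Only Radiographs that are determined to be of sufficient quality will go into the radiograph repository". For films that fail, "feedback will be provided to the Node Coordinator to pass along to the practitioner to correct the acquisition of future radiographs". Sections 4 and 7.1 add that the study team will also look for a better film.
- Missing outcomes (Protocol 11.3, Missing data): multiple imputation if missing at random holds and missingness is 10% to 50%, reported beside a completers-only analysis.

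**The concern.** A change from baseline exists only if the baseline level exists. When the baseline film is rejected and no substitute is found, the outcome is undefined at Years 1, 2 and 3, however good the later films are. Yet two or more later readable films carry information on the rate of bone loss, and a mixed model can use it if the response is the bone level itself. The plan chooses a longitudinal model and then gives it a response that sets this information aside.

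At stake is the precision of the risk-factor analysis for bone-loss progression, and the number of implants that inform it. The films are taken for clinical care, so the study does not plan a repeat exposure when one fails.

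**Working it through.** **No stated figure to reproduce.** Tables 1 and 2 in section 11.2 concern proportions. The protocol gives no film-rejection rate, standard deviation or power for mm bone loss, so the sizes below rest on assumptions.

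**Inputs.**
- Implants: 1960 = 1400 (first column of Table 1) x 1.4 (cluster size stated with Table 2).
- Films: four per implant, at years 0, 1, 2 and 3 (protocol).
- Assumed: each film readable with probability q = 0.9, 0.8 or 0.7, independently; reading SD 0.3 mm (variance 0.09); between-implant variance 0.5 mm2; slope SD s from 0 to 0.2 mm/year. Clustering by patient and practitioner is left out.

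**Step 1: implants that can inform the slope.**
- Change from baseline needs the baseline film and at least one later film: q[1 - (1-q)^3].
- Bone level needs any two of the four films: 1 - (1-q)^4 - 4q(1-q)^3.

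| q | change | level | difference x 1960 |
|---|---|---|---|
| 0.9 | 0.9 x 0.999 = 0.8991 | 1 - 0.0001 - 0.0036 = 0.9963 | 0.0972 x 1960 = 191 |
| 0.8 | 0.8 x 0.992 = 0.7936 | 1 - 0.0016 - 0.0256 = 0.9728 | 0.1792 x 1960 = 351 |
| 0.7 | 0.7 x 0.973 = 0.6811 | 1 - 0.0081 - 0.0756 = 0.9163 | 0.2352 x 1960 = 461 |

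**Step 2: variance of the estimated annual change.** For each of the 16 film patterns, take t as the years of the readable films, I as the identity matrix and J as the all-ones matrix.
- Level model: V = 0.5 J + s^2 tt' + 0.09 I. Information is Z'V^-1 Z with Z = (1, t).
- Change model (baseline readable, later years only): W = s^2 tt' + 0.09 (I + J). Information is t'W^-1 t. The J term is the shared baseline reading error, so the change model is given its correct covariance.

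Weight each pattern by its probability, sum, invert, and take the slope variance. The ratio of change to level, from s = 0 to s = 0.2, is:
- all films readable: 1.00 throughout
- q = 0.9: about 1.04 to 1.08
- q = 0.8: about 1.09 to 1.16
- q = 0.7: about 1.14 to 1.25

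**Step 3: readability clustered within implants.** With beta-binomial readability at mean 0.8, a film correlation of 0.4 leaves 187 implants regained and a ratio of 1.05 to 1.09. A correlation of 0.6 leaves 117 and 1.03 to 1.06.

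**Step 4: cross-check under other assumptions.** Take 2000 implants with all later films accepted, random-intercept SD 0.6-1.0 mm, slope SD 0.05-0.3 mm/year and residual SD 0.2-0.3 mm. The excess variance is then 5-9% if 10% of baseline films are rejected, 11-21% at 20% and 19-36% at 30%. The direction is the same. The figures are higher partly because no later film is lost.

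**Step 5: when imputation would apply.** Under independent films, the change at a given visit is missing with probability 1 - q^2: 19% at q = 0.9, 36% at 0.8 and 51% at 0.7. Counted this way, the first two fall inside the 10% to 50% band and the third falls just outside. The protocol does not say how the rate is counted.

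**The case against.** The strongest objection is that the plan already has two remedies. The study team looks for a better film, and missing outcomes are multiply imputed. A reader might infer that an implant without a baseline film contributes nothing, or that a rejected baseline film usually stays lost. The documents support neither. A substitute may be found, and inside the imputation band such implants enter through imputed values. What remains is that success in finding a film is not assured and that imputation is conditional. Imputing the change from the analysis covariates alone adds no information. It helps only if the later bone levels are used as auxiliary data, which the protocol does not state.

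A second objection is that section 11.3 does not fix the model terms, and a statistical analysis plan could model bone level against time. That is so, but the protocol itself names bone loss as the outcome and twice defines it as a change. Its plain reading is therefore a change-score response.

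A third is that the gain is small. That stands: even a ratio of 1.25 widens the standard error by only about 12% (square root 1.118), and at q = 0.8 with independent films by about 4-8%. Counts such as 351 implants look larger than the precision they bring.

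Two further readings are tempting. One is that the single baseline reading error, carried into all three changes, costs precision by itself. It does not: with all films readable the ratio is 1.00 when the covariance is modelled correctly. The other is that the loss is selective by jaw region or practice. The quality criteria make this conceivable, but nothing in the documents shows it and no bias has been quantified.

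**Conclusion.** The point holds as one of efficiency. By the protocol's own definition, an implant whose baseline film is rejected and not replaced has no observed progression outcome, although bone level is measured on each of its later films that passes review (not on every later film). Such implants are absent from the completers-only analysis, and imputation may recover little of their information.

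Under the stated assumptions, the loss is roughly 4-25% in slope variance for independent readability of 0.9 down to 0.7, and 3-9% at 0.8 when readability clusters within implants. These figures take no credit for imputation. The true rejection rate and standard deviations are unknown.

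The analysis affected is secondary in one part of section 11.3 and exploratory, subject to data, in another. A reader should not infer that the planned analysis is invalid or biased. This point does not extend to the binary peri-implantitis outcome, which the change below leaves as it is. It is a low-cost improvement.

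**What to change.** In Protocol 11.3, Secondary Objectives, make the response for disease progression the bone level in mm on every accepted film, at baseline and Years 1 to 3. Include time and risk factor by time terms, a random intercept and slope for implant, and random effects for patient and practitioner. Report the risk factor by time coefficient as mm lost per year, and keep change from baseline as a descriptive summary.

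If change is kept as the response, state at least that bone levels from later accepted films enter the imputation model.

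The cost is wording in the protocol and the statistical analysis plan. No new data, films, site work or software are needed.

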4 STUDY DESIGN

- This is a prospective, observational 3-year cohort study of patients who undergo dental implant restoration by practitioners of the National Dental PBRN. Practitioners who restore dental implants will recruit and enroll their patients in this cohort study during the prosthetic phase of implant therapy.
- Approximately 200 practitioners from all 6 Network Nodes (approximately 35 practitioners per Node) will participate in the study, with each practitioner contributing approximately 10 patients and a maximum of approximately 50 implants.
- The patient population will comprise patients who plan to receive dental implant restorations provided by practitioners of the National Dental PBRN. Approximately 1550 patients will be enrolled until approximately 2000 implants are available for longitudinal observation. Implants will be clustered within patients and within approximately 200 dental practitioners across network practices. Each enrolled patient can contribute more than one implant if multiple implants will be restored at the baseline visit.
- Practitioner and practice characteristics from the National Dental PBRN Enrollment Questionnaire will be combined with data collected for this observational study.
- The prospective, observational study design will allow an opportunity to inform our knowledge of parameters for implant success and risk factors for biologic and prosthetic complications associated with implant therapy. The study will describe the implant restorative therapy provided by the practitioners, the incidence and prevalence of biologic and prosthetic complications, and will correlate patient-level factors, prosthetic- and implant-level characteristics with the risk for implant complications and the therapies provided for dental implant complications.

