Bone Grafting at time of implant placement	biologic complications
Immediate loading	biologic complications
Reason for tooth loss: Periodontitis	biologic complications
Reason for tooth loss: Endodontic failure	biologic complications
Reason for tooth loss: Caries	biologic complications
Reason for tooth loss: Trauma	biologic complications
Congenitally missing	biologic complications
Removable prosthesis	biologic complications
Poor prosthetic fit	biologic complications
Emergence angle	biologic complications
Cement remnants present	biologic complications
Open contacts present	biologic complications
Single tooth restoration	biologic and prosthetic complications
Multiple unit restoration splinted	biologic and prosthetic complications

Cemented restoration	biologic and prosthetic complications
Custom abutment	biologic and prosthetic complications
Stock abutment	biologic and prosthetic complications
Removable prosthesis full arch	prosthetic complications
Removable prosthesis: poor retention	prosthetic complications
Screw retained prosthesis	prosthetic complications
Opposing dentition: Natural	prosthetic complications
Opposing dentition: Complete denture	prosthetic complications
Opposing dentition: Partial denture	prosthetic complications
Occlusion: Mutually protected	prosthetic complications
Occlusion: Group function	prosthetic complications
Prosthesis material: Porcelain	prosthetic complications
Prosthesis material: Zirconia	prosthetic complications
Prosthesis material: Plastic	prosthetic complications
Prosthesis material: Zirconia with Porcelain veneer	prosthetic complications

Tertiary (exploratory) Objectives. To explore the OHRQoL (Oral Health-Related Quality of Life) following implant therapy, and to explore patient/implant/therapy level factors associated with patient satisfaction and OHRQoL.

The data from the OHRQoL will be used to quantify overall satisfaction with implant therapy and quality of life post-implant therapy, and will be presented at each time point to explore any potential time trend. In addition to baseline demographics and clinical factors, the type and location of prosthesis as well as the different types of complications will be included in correlation analysis with the OHRQoL survey data (Table 2). Because the OHRQoL score is a continuous variable, mixed effects model will be used to examine the association between these patient/implant/therapy factors and the OHRQoL score to account for the longitudinal nature of the data.

Table 4.

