Patient level factors
Age at baseline
Diabetes Mellitus
Smoking status
Peri-implant mucositis
Peri-implantitis
Implant failures
Periodontitis diagnosis
Gingivitis diagnosis
Parafunctional habits

Implant/ Prosthesis level factors
Removable partial prosthesis
Poor prosthetic fit
Fixed prosthesis
Open contacts present
Single tooth restoration
Multiple unit restoration splinted
Cemented restoration
Screw retained prosthesis
Custom abutment
Stock abutment
Removable prosthesis full arch
Fixed full arch prosthesis
Prosthesis material: Porcelain
Prosthesis material: Zirconia
Prosthesis material: Plastic
Prosthesis material: Zirconia with Porcelain veneer

Practitioner level factors
Number of implants restored per month
Years in practice
Post graduate education
Specialty training

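### The person-level Poisson model for prosthetic complication counts tests practitioner factors with no stated allowance for practitioner clustering, overdispersion or unequal follow-up

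*Protocol*

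**What the plan says.** Protocol Section 4 describes the hierarchy: "Implants will be clustered within patients and within approximately 200 dental practitioners across network practices". Section 11.3 (Secondary Objectives) repeats it: "Multiple implants/ prostheses are clustered within the same patient, and multiple patients clustered within practitioners". It then ties a method to it, for the binary outcomes: "To account for these correlations, General Estimating Equations (GEE) will be used to identify practitioner, patient and implant variables".

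The following paragraph of Section 11.3 specifies two further risk-factor models.

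- **Number of prosthetic complications over three years:** "The unit of analysis will be at the person level, and Poisson models will be used to identify practitioner, patient and prosthesis risk factors". Nothing is said about correlation within practitioner, the variance assumption or time at risk.
- **Bone loss in mm:** a mixed effects model to "account for the longitudinal nature of the data and to identify the practitioner, patient and implant risk factors".

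Under the tertiary objectives, a mixed model relates "patient/implant/therapy factors and the OHRQoL score to account for the longitudinal nature of the data". That sentence does not mention practitioner factors, but Table 4 lists four of them.

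The same four practitioner factors appear in Table 3, each marked for prosthetic complications: "Number of implants restored per month", years in practice, postgraduate education and specialty training.

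**The concern.** The protocol states a three-level structure, says how one analysis will respect it, and then fixes a neighbouring analysis without that provision. The gap matters most where the factor under test is a property of the practitioner. All of a practitioner's patients share its value, so the effective sample for that factor lies nearer the 200 practitioners than the 1550 patients. A plain Poisson model takes the patients as independent.

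A non-zero practitioner correlation is plausible for this outcome. Under Sections 3.1 and 7.1, the practitioners who insert the prostheses also record whether a prosthetic complication has occurred. At stake is whether experience, training or volume is reported as a risk factor for repeated complications more often than the nominal 5% allows.

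Two features of the outcome add to this. Repeated complications in one patient tend to be more variable than a Poisson variance allows. Time at risk also differs between patients: Section 4 says that some patients may not complete every visit and that a removed implant has no further study visits.

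**Working it through.** **1. The protocol's only figure that allows for clustering.** Table 2 (Section 11.2) gives detectable prevalences for the binary outcomes.

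- Stated inputs: two-sided 5%, equal categories, cluster size 1.4.
- Assumed inputs: 80% power (not stated) and 1400 × 1.4 = 1960 implants, taking 1400 from Table 1.
- Formula: n per group = (1960/2)/DE, with DE = 1 + (1.4 − 1) × ICC, in the usual two-proportion calculation.
- ICC 0.1: DE = 1.04, n = 942. Detectable 56.44% (table 56.43%) and 25.40% (table 25.40%).
- ICC 0.5: DE = 1.20, n = 817. Detectable 56.91% (table 56.90%) and 25.82% (table 25.81%).

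All ten cells agree within 0.02 percentage points; 90% power is about one point off. A cluster size of 1.4 is on the scale of implants per patient (2000/1550 = 1.29), so Table 2 carries no practitioner level. It also does not cover the count model.

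**2. Cluster size for the count model.** The unit is the person, so m = 1550/200 = 7.75. Section 4 also gives about 10 patients per practitioner, so m = 10 is shown for comparison.

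**3. Error rate for a factor constant within practitioner.** DE = 1 + (m − 1) × ICC; true SE / model SE = √DE; actual alpha = 2 × [1 − Φ(1.96/√DE)]. For m = 7.75 and ICC 0.05: DE = 1 + 6.75 × 0.05 = 1.3375, √DE = 1.157, 1.96/1.157 = 1.69, alpha = 9.0%. The protocol gives no practitioner ICC, so the range is assumed.

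| Assumed ICC | DE (m = 7.75) | True / model SE | Actual alpha (m = 7.75) | Actual alpha (m = 10) |
|---|---|---|---|---|
| 0.01 | 1.067 | 1.033 | 5.8% | 6.0% |
| 0.02 | 1.135 | 1.065 | 6.6% | 7.1% |
| 0.05 | 1.337 | 1.157 | 9.0% | 10.4% |
| 0.10 | 1.675 | 1.294 | 13.0% | 15.5% |
| 0.20 | 2.350 | 1.533 | 20.1% | 24.1% |

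These rows assume equal cluster sizes. Section 4 allows up to about 50 implants per practitioner, and unequal sizes raise the design effect.

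**4. Check by simulation under the null, 200 practitioners × 8 patients.**

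- Linear model ignoring practitioner: 6.3%, 9.5% and 13.4% at ICC 0.02, 0.05 and 0.10, in line with the table.
- Plain Poisson, assumed mean 0.3 events per person: 5.1%, 7.5%, 15.1% and 23.6% at practitioner log-rate SD 0, 0.3, 0.5 and 0.7. This scale differs from the ICC, so it does not match the table row by row.
- The same Poisson data with practitioner-clustered standard errors: 5.5% to 7.1%.
- A factor that varies randomly within practitioner, practitioner ignored: about 5%.

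**5. Overdispersion and follow-up.** If the count variance is φ times its mean, the model SE is too small by √φ for every factor, not only practitioner factors. The protocol gives no basis for φ, so no figure is attached. On exposure, a patient followed for one year has, at a constant rate, one third of the expected count of a patient followed for three. Without an offset, that difference is read as a difference in risk.

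**The case against.** The strongest reply is that random effects, robust variance, dispersion and offsets are commonly left to the statistical analysis plan, which is not shown.

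**For the mixed models this stands.** A reader might infer that the bone-loss and OHRQoL models handle repeated measures and nothing else. The text does not support that. It gives one purpose for each model, lists no random effects and excludes none, and this class of model can carry practitioner, patient and implant effects without a change of name. Shared measurement habits are also a weak argument here: bone levels are read centrally by two calibrated evaluators blinded to each other (Section 7.3), and OHRQoL is reported by patients.

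**For the count model it stands only in part.** Section 11.3 is as specific here as for the binary outcomes, giving unit, model family and factors. It treats correlation as a reason for choosing GEE in one paragraph and does not mention it in the next. A person-level Poisson model has no within-practitioner term unless one is added.

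Other replies:

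- Analysis by person already removes implant-within-patient clustering. This is correct; only the practitioner level remains.
- Section 11.3 promises to check that distributions meet model assumptions. That might reveal overdispersion, but it fixes no response and does not address clustering.
- Section 3.1 mentions a Poisson model per implant and year of follow-up. That concerns the incidence estimates and is not carried into the risk-factor count model.
- A reader might extend the point to all risk factors, including prosthesis type. The calculation applies to factors constant within practitioner. A prosthesis factor is affected only to the extent that practitioners favour one type.
- The analyses are secondary or exploratory. This is correct, and it limits the weight of the point.

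**Conclusion.** The point holds for the Poisson count model. Run as worded, its tests of the four practitioner-level factors are too liberal whenever the practitioner ICC exceeds 0. The true error of a nominal 5% test is about 6.6%, 9.0% and 13.0% at assumed ICCs of 0.02, 0.05 and 0.10 with equal clusters of 7.75 patients; at 0.01 it is 5.8%, which is minor. The direction is certain for a positive ICC; the size is not, because the documents give none. Overdispersion would add to this and would reach all factors in that model.

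It does not hold as a finding that standard errors in the bone-loss and OHRQoL models are too small. There the wording is incomplete and should be made consistent. If several implants per patient were treated as independent in the bone-loss model, patient-level factors would be affected too, but nothing says that they will be.

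The main binary risk-factor analyses already use GEE, and the primary incidence point estimates are not affected. The change is worth making because identifying risk factors is a secondary objective and the repair is cheap.

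**What to change.** In Section 11.3, amend the count-model sentence to state three things:

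- GEE or a robust variance clustered on practitioner, or a practitioner random effect.
- A negative binomial or quasi-Poisson variance.
- Log follow-up time as an offset.

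For consistency, add that the bone-loss mixed model includes practitioner, patient and implant random effects, and that the OHRQoL mixed model includes practitioner and patient random effects. Align the OHRQoL sentence with Table 4 by saying whether practitioner factors are examined.

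The cost is a few sentences of analysis wording; data collection is unchanged. Intervals for practitioner-level factors in the count model widen by the ratios in the table, about 7%, 16% and 29% at ICC 0.02, 0.05 and 0.10 (√DE = 1.065, 1.157, 1.294). About 200 practitioners is a workable number of clusters for a robust variance: in the simulation it held the error at 5.5% to 7.1%.
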